### 3.4/ Informed Consent

Patients found on screening to qualify for enrollment in CHILL-pilot and whose ICU provider agrees will be offered participation in CHILL-pilot. Because eligible patients will be seriously ill, on high levels of mechanical ventilation, and receiving sedation and possibly NMB, informed consent will be obtained from the patient’s LAR by Drs. [name] or [name], the CHILL-pilot Study Coordinator, or other Clinical Team member. CHILL-pilot study personnel who are also responsible for the clinical care of a potential subject will not participate in the consent discussion to avoid undue pressure. The information provided in the consent will cover the elements listed in the 21 CFR Part 50.25 and be approved by the UMB IRB. This includes the investigational nature and objectives of the trial, the procedures and treatments involved and their attendant risks, discomforts, and benefits, and potential alternatives including not participating and right to withdraw without penalty. Study staff personnel will offer to answer any questions. Consent will be documented by LAR signature on the IRB approved consent form LAR. No study procedure will be done prior to obtaining signed informed consent. Once patients regain decision making capacity as assessed using an IRB-approved Capacity Assessment tool, informed consent for continuing participation in CHILL-pilot will be obtained by the Drs. [name] or [name] or a Clinical Team member.

If the patient does not have capacity to provide informed consent and the LAR cannot be present in the hospital, we will pursue informed consent remotely through one of the following modalities: (a) telephone; (b) email; (c) FAX.

1. Initial Contact: The LAR will be identified from the patient’s electronic record and contacted initially by telephone. The team member will call from a private location with access to a non-team member witness (for verbal consent). The team member will identify themselves, confirm that the person on the line is the LAR, and state that they are calling to discuss having the patient participate in a research study. They will then offer to provide information to the LAR verbally or by FAXing or emailing a copy of the consent form.

2. Verbal phone consent: If the LAR selects the verbal consent option, the team member will read the consent form over the phone. The LAR will then be given time to ask questions, including the option to do so with a follow up phone call. Once the LAR is ready to give consent, a witness who is not part of the study team will join the call, the LAR will be asked if they any further questions, and consent will be obtained. The team member obtaining consent and the witness will then sign and date on the signature page of the consent form, print the patient's name on the participant name line, and indicate that consent was obtained verbally by checking the appropriate boxes at the bottom of the signature page. They will complete the LAR affidavit, sign page 1, and write verbal consent on the LAR signature line on page 2 and the witness will sign page 1.

3. FAX option: If the LAR selects the FAX option, they will provide a secure FAX number and a time and contact phone number for the team member to call to discuss the study and answer questions. The team member will FAX the consent form and page 2 of the LAR affidavit to the FAX number provided. To minimize loss of confidentiality, the consent form will be sent to the LAR without the patient's name included. They will call the LAR back at the established time, confirm that the LAR received all pages of the consent form and that they are legible. They will then discuss the study and answer questions (referring to appropriate pages in the consent form) as described for verbal consent. If the LAR is then willing to give consent, they will be asked to enter the patient's name on the participant name line, sign and date on the LAR signature line of the signature page, complete and sign page 2 of the LAR affidavit, and FAX the signed signature page of the consent form and LAR affidavit page 2 back to a secure FAX number where the LAR will be waiting. Alternatively, the LAR will be given the option of taking a picture of the signed signature page with their cell phone and emailing it back to the team member.

4. Email option: If, after advised of the possible loss of confidentiality with email transmission of the consent form, the LAR selects the email option, they will be asked for an email address and a time and phone number for a follow-up discussion of the study. The team member will send an email with a pdf file of the consent form and page 2 of the LAR affidavit attached to the email address provided by the LAR. To minimize loss of confidentiality, the consent form will be sent to the LAR without the patient's name included. A follow-up phone call will be conducted as discussed for FAX consent. If the LAR is then willing to give consent, they will be asked to print out the signature page of the consent form, enter the patient's name on the participant name line, sign and date on the LAR signature line, complete and sign page 2 of the LAE affidavit, take a picture of the signed consent form signature page and LAR page 2 with their cell phone, and email it back to the team member. Alternatively, the LAR will be given the option of FAXing the signed signature page back to the team member.

For emailed consent, the team member will print a hard copy of the emailed images. For the FAXed and email hardcopies, the team member will confirm that the patient's name is legibly recorded on the participant's signature line, sign and date on the Investigator signature line, and note how the consent was obtained by checking the appropriate boxes on the consent form. They will complete page 1 of the LAR affidavit and confirm that page 2 is adequately completed.

Electronic images of the signed signature page of the consent form and the LAR affidavit will be placed in the electronic medical record.

### 3.5/ Retention Strategies

We anticipate that most participating subjects will remain hospitalized, likely in the ICU, through study day 7 and accessible to study personnel. Patients will be seen daily by study personnel through the first 7 days for data collection, protocol adherence, and collection of research samples. Beyond study day 7 patient status will be monitored by examining the medical record and, as needed, bedside visit. Study personnel will complete CRFs for ICU discharge, study day 28 status, and hospital discharge. The hospital discharge CRF will contain patient disposition and contact numbers, including the patient's LAR to facilitate 60-day and 90-day follow-up.

### 3.6/ Safeguards for Vulnerable Population

All potential CHILL-pilot subjects will be considered vulnerable because they will be cognitively impaired as a result of their illness and treatment. Informed consent will be obtained from an LAR and subjects will be re-consented once they regain decision-making capacity as determined using a capacity assessment tool that has been approved by the UMB IRB. Prisoners and pregnant women are excluded. Rules for early termination of hypothermia and NMB have been developed.

### 3.7/ Outreach to Minorities and Women

The expected COVID-CHILL-pilot patient population is well-represented in minorities and women. Based on our experience with ARDSNet, we expect our study composition to be ~44% African American, 9% Hispanic, and 45% white and ~50% female. The composition of the 64 patients in our CHILL retrospective and open-label pilot study 38 was 60.9% Caucasian, 34.4% African American, 4.6% Hispanic, and 3.1% Asian, and 41% female. There are no exclusions based on race, ethnicity, or gender. Pregnancy will be an exclusion because there are no data to insure safety of mild hypothermia for the fetus. Pregnancy testing will be performed in all women of child-bearing age prior to enrollment.

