### 3.2.2 Exclusion Criteria

1. Missed ARDS window (>48hrs)
2. Missed mechanical ventilation window (>7 days)
3. Refractory hypotension (> 0.2 mcg/kg/min of norepinephrine or equivalent dose for minimum of 6 h)
4. Core temperature <35.5°C while not receiving CRRT
5. Patient is unable to give consent and no legally authorized representative is available;
6. Significant, active bleeding (>3u blood products and/or surgical/IR intervention)
7. Platelets <10K/mm^3 (uncorrected)
8. Active hematologic malignancy
9. Skin process precludes cooling device
10. Moribund, not likely to survive 72h
11. Pre-morbid condition makes it unlikely that patient will survive 28 days
12. Do Not Resuscitate status
13. Not likely to remain intubated for ≥48h
14. Physician unwilling to participate
15. Severe underlying lung disease
  - a. On home O2
  - b. On BIPAP (except for OSA)
  - c. Prior lung transplantation
16. BMI >45 kg/m^2
17. Known NYHA class IV heart disease
18. Acute Coronary Syndrome past 30 days (MI, unstable angina)
19. Cardiac arrest within 30 days of enrollment
20. burns over >20% of the body surface
21. severe chronic liver disease (Child-Pugh of 12-15)
22. Previously randomized in CHILL study

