## 4/ Screening

Refer to Screening Worksheet and Screening CRF. All patients in participating ICUs (UMMC MICU, T6S, 10W) who are 18-65 years old, have a PCR-documented COVID diagnosis and intubated or have a tracheostomy in place and have been receiving mechanical ventilation for <7 days will be evaluated for enrollment using the Screening Worksheet. If any of the

disqualifying exclusion criteria listed on the Screening/enrollment/randomization CRF are identified, the patient will be excluded. Otherwise they will be evaluated for inclusion criteria and enrolled or followed until they meet inclusion criteria or exit the inclusion window. The 3-digit study ID number and a unique 3-letter patient identifier will be supplied by the on-line Screening Log Tool (on the UMB OneDrive). Demographic information and final enrollment status, and the reason for exclusion (if applicable) will be entered in the on-line screening log and on the Screening CRF along with the 3-digit study ID and 3-letter patient identifier. Those patients who meet enrollment criteria will be offered enrollment. We anticipate that all consent will be obtained from the patients’ Legally Authorized Representative (LAR). If consent is obtained, the patient will be enrolled and the “Yes” box about consent (line 11) will be checked. If the patient meets enrollment criteria but consent cannot be obtained, the patient will be excluded from the study.

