### 6/ Study Visit Schedule/Schedule of Events (see Gantt chart below)

DAYS	-2	0	1	2	3	4	7	8-27	28	ICU DC	Hospital DC	60	90
Screening data, consent, enrollment, monitor for randomization	X												
Pregnancy test (F)		F											
Randomization, baseline data, start assigned temperature management		X											
Q2h vital signs (e.g. SpO2, mean airway pressure, core temperature)		X	X	X	X	X	X						
Temperature management protocol		X	X	X	X								
ABGs		A	A	A	A	A	A						
Basic metabolic panel, CBC (times per day)		2	2	2	2	2	1						
Blood sugars (times per day)		4	4	4	4	A	A						
Research blood sample collection		X	X	X	X	X	X						
Ventilator and respiratory parameters	X	X	R	R	R	R	R						
Fluid management		X	X	X	X	X	X						
NMB status	X	X	X	X	X	X	X						
Medication review (pressors, steroids, inhaled vasodilators)		X	X	X	X	X	X						

Monitor for AEs		X	X	X	X	X	X	X	X	x	x	X	X
Calculation 28-day VFDs, ICU-FDs									X				
MOCA										X	X		
Assess Vital and functional status		X	X	X	X	X	X	X	X	X	X	X	X

X = Required (time not specified)

A = When Available

R = Measured during daily reference measurements (0600-1000). When more than one value is available, the value obtained closest to 8 a.m. will be recorded.

F = Required on females of reproductive age.

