## Screening/Enrollment/Randomization Source Document

Obtain screening number and complete this form for all patients 18-65 years old with a confirmed COVID-19 diagnosis, intubated or trached and ventilated for < 7 days.

Screening Completed by \_\_\_\_\_

Date/Time of Initial Screen: 

MONTH	D	D

 / 

Y	Y	Y	Y	Y	Y

 / 

TIME (0-2400)			

Type of Unit:  Medical     Surgical     Med/Surg     Trauma     ED

Gender (at birth):  Male     Female      Date of Birth: 

MONTH	D	D

 / 

Y	Y	Y	Y	Y	Y

**Ethnicity:**  Hispanic or Latino     Not Hispanic or Latino

**Race:** Asian:  Yes     No    Native Hawaiian/Pacific Islander:  Yes     No    White:  Yes     No  
 Black/African American:  Yes     No    American Indian/Alaskan Native:  Yes     No  
 Not reported:  Yes     No

Date first positive SARS-CoV-2 test 

MONTH	D	D

 / 

Y	Y	Y	Y	Y	Y

If subject meets any of the following exclusion criteria, they are excluded and you can STOP here and complete the screening log entry, otherwise proceed to Berlin criteria checklist./

- Moderate-severe ARDS (bilateral infiltrates and P/F < 200) present for >48hrs
- Missed NMB window: (>12 hrs)
- Missed mechanical ventilation window (>7 days)
- Refractory hypotension ( > 0.2 mcg/kg/min of NE or equivalent dose for a minimum of 6 h)
- Core temperature <35.5°C while not receiving CRRT
- No Legally authorized representative
- Significant, active bleeding
- Platelets <10K (uncorrected)
- Active hematologic malignancy
- Skin process precludes cooling device
- Moribund, not likely to survive 72h
- Pre-morbid condition makes it unlikely that patient will survive 28 days
- Do Not Resuscitate status
- Not likely to remain intubated for ≥48h
- Physician unwilling to participate
- Severe underlying lung disease
  - On home O2
  - On BIPAP (except for OSA)
  - prior lung transplantation
- BMI >45
- Known NYHA class IV heart disease
- Acute Coronary Syndrome (MI, unstable angina)
- Cardiac arrest within 30 days of enrollment
- Burns over >20% of the body surface
- Previously randomized in CHILL study
- Severe chronic liver disease (Child-Pugh score of 12-15)Berlin Criteria checklist:

SITE ID		PATIENT ID				LETTER CODE		

Starting from the first ventilator day, answer questions until patient is enrolled and randomized or exceeded 7 ventilator days. For each day record the date/time of the first positive study.

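### Pregnancy and prisoner exclusions stand in the protocol's narrative but not in its exclusion list or on the screening form that decides eligibility, and the timing of the pregnancy test is inconsistent

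*Protocol*

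**What the plan says.** **The exclusions.** Protocol Section 3.6 says: "Prisoners and pregnant women are excluded". Section 3.7 gives the reason for the pregnancy exclusion: "Pregnancy will be an exclusion because there are no data to insure safety of mild hypothermia for the fetus". It then sets the timing of the test: "Pregnancy testing will be performed in all women of child-bearing age prior to enrollment".

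**The list.** Section 3.2.2 numbers 22 exclusion criteria, the last being "Previously randomized in CHILL study". Neither pregnancy nor prisoner status is among them.

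**The form.** Line 9 of the Screening/Enrollment/Randomization Source Document opens its checklist with "If subject meets any of the following exclusion criteria, they are excluded and you can STOP here and complete the screening log entry". The checklist names neither condition.

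**The schedule.** Section 6 marks screening, consent, enrolment and monitoring for randomisation under day -2. It marks the pregnancy test, required for females of reproductive age, under day 0. Randomisation, baseline data and the start of assigned temperature management are also under day 0.

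**The concern.** An exclusion protects patients only if it reaches the step at which someone decides eligibility. Here two exclusions are stated in sections on vulnerable populations and outreach, which a screener filling in a form at the bedside may not consult. The same two are missing from the list and the form that the screener does use.

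The protocol itself presents the pregnancy exclusion as a matter of fetal safety. Section 3.4 has consent given by a legally authorised representative because eligible patients will be seriously ill and sedated. The patient will usually be unable to volunteer the information, so a written check carries more weight than in most trials. Cooling is to start as soon as possible after assignment (Section 5), which leaves little time to catch an omission later.

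**Working it through.** No sample size, power or error rate is involved. The check is to follow one patient through the documents and look for a point at which pregnancy or incarceration would stop her.

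| Step | Where | What is asked | Pregnancy or incarceration checked? |
|---|---|---|---|
| Inclusion | Section 3.2.1 | Men and women aged 18-65, with clinical criteria | No |
| Exclusion list | Section 3.2.2 | 22 items | No (0 of 22) |
| Exclusion decision | Section 4; form line 9 | Items on the form's checklist | No |
| Eligibility summary | Form line 11 | Berlin elements, and no exclusion on the checklist | No; it only points back to the checklist |
| Consent | Form line 12 | Yes or no | No |
| Randomisation criterion | Form lines 13-14; Sections 5 and 10.1 | PEEP and P/F ratio, then baseline blood and assignment | No |
| Assignment tool | Section 3.3.2 | Investigator name, study ID, letter code, proning status | No |
| Baseline record | Baseline Data form | History, vital signs, laboratory values | No result field |

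**Is the form really the gate?** Section 4 says that if any of the "disqualifying exclusion criteria listed on the Screening/enrollment/randomization CRF are identified, the patient will be excluded"; otherwise the patient is assessed for inclusion and either enrolled or followed. Section 10.1 gives the same instruction: with no listed exclusion present, go on to the Berlin checklist and then to consent. Both tie the decision to what is printed on the form.

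**Timing.** Four statements have to be read together.

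1. Section 3.7: the test comes before enrolment.
2. Section 6: the test is on day 0, the randomisation column; consent and enrolment are under day -2.
3. Section 5: a patient who already meets the P/F criterion is enrolled and randomised at the same time. For that patient enrolment is also on day 0.
4. Sections 3.4 and 4: no study procedure precedes signed consent, and obtaining consent leads to enrolment.

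Statements 1 and 2 conflict for a patient enrolled ahead of randomisation. For a patient enrolled and randomised together they need not conflict, but nothing fixes the order within day 0. Statements 1 and 4 are also in tension: if consent leads directly to enrolment, a test done only for the study and before enrolment may fall before consent, unless a routine-care result already exists.

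**Size.** Section 3.7 expects about 50% women, and the earlier cohort of 64 had 41%. With 20 patients this is 0.50 × 20 = 10, or 0.41 × 20 = 8.2, so about 8 to 10 women aged 18-65. The documents give no figure for child-bearing age, pregnancy or incarceration.

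**The case against.** The best defence is that the safeguard exists. The pregnancy exclusion is stated twice, the prisoner exclusion once, and the schedule marks the test as required. Staff who follow the schedule would test, and to randomise a patient known to be pregnant they would have to disregard Sections 3.6 and 3.7. This stands as far as it goes: the fault is an internal inconsistency, not a missing rule. It does not supply the link from a test result to the decision to randomise.

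Section 4 also mentions a Screening Worksheet, and the online log in Section 3.1 has a pulldown of exclusion reasons. The contents of neither are shown, so either might cover these conditions. That limits how confidently one can say what screening would pass in practice. Even so, Section 4 names the form's list as the basis for exclusion.

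For prisoners, Section 12 makes incarceration of a subject reportable to the IRB. That acts after the event and does not screen anyone out.

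Three stronger readings are tempting, and the documents do not support them:

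- **The test is always scheduled after enrolment.** Enrolment can coincide with randomisation on day 0, and the order within that day is open, so the test could still come first.
- **Compliance cannot be audited.** No trial form shown has a field for the result, but source documents are kept (Data Management section) and a result may be in the medical record. What is missing is an audit trail on the forms.
- **About 10 of 20 patients are exposed to the error.** That is the expected number of women of any eligible age, not an estimate of exposure.

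**Conclusion.** The concern holds as an inconsistency with a safety consequence. Two exclusions that the protocol states are absent from its formal list and from the form that decides eligibility. No step up to and including the assignment tool asks for a pregnancy result or incarceration status, so a form completed without error could lead to randomisation of a patient whom Sections 3.6 and 3.7 exclude. Separately, the timing of the test is not stated consistently, and the place given in Section 3.7 may not fit the consent rules.

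The likelihood of such a randomisation cannot be quantified from the documents. The conclusion assumes that the unseen worksheet and pulldown do not fill the gap; if they do, the list, form and schedule would still need to be brought into line. It does not depend on showing that the test would be omitted or done late, only that nothing requires its result to be seen before assignment.

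**What to change.** 1. Add pregnancy and prisoner status to Section 3.2.2 and to the exclusion checklist at line 9 of the screening form. Use the same entries in the Screening Worksheet and the online log's pulldown if they are not already there.
2. Add a field to the screening form for the pregnancy-test result and its date, with a not-applicable option for patients who do not need the test.
3. State in Sections 3.3.2, 5 and 10.1, and at line 14 of the form, that this result must be recorded before the assignment tool is opened.
4. Reconcile the timing of the test across Sections 3.4, 3.7, 4, 5 and 6. The sponsor should say how the test relates to consent, enrolment and randomisation, and whether a routine-care result may be used. Simply moving the test ahead of enrolment in the schedule could put a study procedure before consent.

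The exclusions and the test are already the sponsor's own, so items 1 to 3 are edits to the list, form and instructions. Item 4 needs a decision as well as an edit. None of it changes the design, the sample size or the analysis.

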### 3.8/ Engagement of Clinical Community to Encourage Recruitment

Presentations about CHILL-pilot will be given as Medical and Pulmonary Grand Rounds at UMMC and to the UMMC critical care committee. Drs. [name] and [name] and coordinator will educate staff and physicians for all participating ICUs about the CHILL-pilot trial. Signs with information about the CHILL-pilot trial including inclusion and exclusion criteria and easy contact information will be prominently displayed in all participating ICUs.

## 4/ Screening

Refer to Screening Worksheet and Screening CRF. All patients in participating ICUs (UMMC MICU, T6S, 10W) who are 18-65 years old, have a PCR-documented COVID diagnosis and intubated or have a tracheostomy in place and have been receiving mechanical ventilation for <7 days will be evaluated for enrollment using the Screening Worksheet. If any of the

disqualifying exclusion criteria listed on the Screening/enrollment/randomization CRF are identified, the patient will be excluded. Otherwise they will be evaluated for inclusion criteria and enrolled or followed until they meet inclusion criteria or exit the inclusion window. The 3-digit study ID number and a unique 3-letter patient identifier will be supplied by the on-line Screening Log Tool (on the UMB OneDrive). Demographic information and final enrollment status, and the reason for exclusion (if applicable) will be entered in the on-line screening log and on the Screening CRF along with the 3-digit study ID and 3-letter patient identifier. Those patients who meet enrollment criteria will be offered enrollment. We anticipate that all consent will be obtained from the patients’ Legally Authorized Representative (LAR). If consent is obtained, the patient will be enrolled and the “Yes” box about consent (line 11) will be checked. If the patient meets enrollment criteria but consent cannot be obtained, the patient will be excluded from the study.

